EAT is of particular relevance to SGLT2i cardiovascular effects because 1) EAT thickness is a strong marker of clinical risk for CVD, including insulin resistance, myocardial lipid content, cardiomyocyte dysfunction^{5,6}, and also fatal and nonfatal coronary events⁷, and 2) SGLT2 treatment in humans decreases EAT mass relative to total body fat, pointing to a potential cardioprotective mechanism^{2,8,9}. Epicardial fat cells are derived from brown adipose tissue during embryogenesis, similar to mesenteric and omental fat cells. As compared with other fat depots, EAT demonstrates a high degree of metabolic flexibility, with increased capacity for FFA uptake, FFA synthesis, lipogenesis, and FFA release in order to meet the changing energy needs of the myocardium¹⁰. Indeed, lipolysis rates of EAT are twice that of visceral fat, and FFA oxidation accounts for 70% of myocardial energy production. Furthermore, because there is no physical barrier between EAT and the vessels that pass through or below the fat, secreted proteins and FFA can diffuse directly into the coronary arteries. EAT secretes a large number of proteins that regulate endothelial function, coagulation, and inflammation: these can be protective or harmful, as evidenced by increased expression of multiple inflammatory cytokines in EAT from individuals with CAD vs controls¹¹ and in depots overlying plaque vs clean vessel¹¹ as well as in those with type 2 diabetes¹².

There is remarkably scant data on the effect of SGLT2i on EAT. SGLT2 receptors have been demonstrated in human EAT², and EAT preadipocytes cultured with dapagliflozin demonstrated enhanced differentiation, decreased chemokine secretion, and increased glucose uptake². In vivo, treatment with dapagliflozin for six months significantly decreased EAT mass compared to controls, along with a significant reduction in TNF- α ⁴, but subjects also lost total body weight which might have accounted for the observations. Two compelling studies in mice demonstrated that 1) empagliflozin promoted fat utilization and browning, and attenuated inflammation and insulin resistance¹³, and 2) ipragliflozin promoted expansion of healthy EAT characterized by decreased inflammation including M1-polarized macrophages¹⁴. Comparable studies have not been done in humans, however, and given the clinical observations of reduced cardiac risk in SGLT2i-treated patients, mechanistic research is warranted.

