2. Test direct effects of ertugliflozin on EAT: Harvest fat from epicardial, pericardial, and subcutaneous (chest wall) depots from patients (with or without CAD and with or without type 2 diabetes) undergoing cardiothoracic surgery. Explants of whole tissue and/or collagenase digested mature fat cells will be used to measure lipolysis (basal/isoproterenol-stimulated/insulin-suppressed conditions), secretome (basal conditions only), and gene expression under mock vs drug-treated culture conditions for 2-24 hours¹⁷. In addition, mature adipocytes freshly isolated from collagenase digestion will be obtained from bariatric surgery patients from both SAT and VAT. This is necessary because bariatric samples yield greater quantities of fat for collagenase digestion whereas epicardial fat sample quantities are smaller which necessitates conducting an explant experiment on the tissue. Mature cells from bariatric samples will be tested for lipolysis, insulin-mediated glucose uptake, gene expression, and inflammatory cytokine secretion under mock vs drug-treated culture conditions for 2-24 hours. VAT has many similar qualities to EAT since they are both visceral depots, and thus will augment any results obtained from EAT and provide a mechanism for isolated mature fat cells which otherwise is not possible. In the case of minimal EAT availability from surgical collection, an explant culture will be performed to differentiate stromal vascular cells into the necessary amount of mature fat cells for a lipolysis assay. This experiment addresses the direct effect of ertugliflozin on EAT in the absence of systemic changes such as lower glucose, insulin, and higher FFA concentrations. Due to small amounts of EAT, we will also conduct lipolysis assays on whole tissue explants from all three depots.

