SVCs are pelleted by centrifugation, erythrocytes lysed, and the isolated cells are seeded onto 12-well plates at a density of 10,000 cells per well for assessment of adipogenesis. Adipogenic differentiation medium purchased from Zenbio (Cat#DM2 for subcutaneous depot cells and #OMDM for visceral depot cells) are used to induce differentiation. ERTUGLIFLOZIN and vehicle are supplemented to the adipogenic differentiation medium. At 3 days, medium is changed to maintenance medium from ZenBio (Cat#AM-1) based on the manufacturer's protocol and ertugliflozin is supplemented. Differentiation is carried out for 14 days to achieve terminal differentiation as described^{17,18}.

6) Optimization of ertugliflozin concentration for pre-adipocyte culture studies

SVC are placed in wells with vehicle control and three different concentrations of ERTUGLIFLOZIN (provided by the company). Planned concentrations to test include 10, 100 and 300nmol/L. Media (with or with drug at the listed concentrations)

will be changed every other day with media replenishment. BrdU can be used to determine the proliferation effect at day 3 and day 7. Optimal concentration will be defined as the concentration that yields 50% of growth inhibition.

7) IMGU using 2NDGB method for cultured adipocytes

Assay of Insulin Mediated Glucose Uptake (IMGU) is carried out after 14 days of adipogenic differentiation. On day 14 terminally-differentiated cells are washed with glucose-free PBS three times to remove the residual glucose in the media. Glucose-free PBS is used to fast the cells for additional one hour at 37C. After one hour incubation, 10ug/ml of insulin is added to the cells to stimulate the glucose release, after 10 mins, 100ug/ml of 2-NDBG solution is added to the cells for fluorescence labeling. 30 mins later, cells are washed with PBS twice to remove the residual 2NDBG in the buffer and cells are lysed in the protein lysis buffer (Sigma, Inc). Subsequently, 100ul of lysis are read by excitation/emission=485/535nm to detect the fluorescence incorporation to the cells. The protein lysis concentration are measured by Coomassie Plus™ Protein Assay. Each samples fluorescence reading is normalized by its protein concentration as the final reading. Each assay is set to have three replicates, mean and SD are calculated compared to the control.

8) Total fat uptake using Oil Red O on day 14 of culture

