Based on prior low carbohydrate diet study, difference to detect between ertugliflozin and control vehicle (mature adipocytes) will be based on differences observed between low and high carbohydrate diets: 0.2 ug FFA release(FFA/ug protein/hour) with SD 0.2, which yields 5 subjects per group for 80% power and alpha 0.05 for unpaired student's t-test (two-tailed). Cell culture with ertugliflozin vs control vehicle: in order to attain statistical power for testing direct actions on EAT from a given subject (comparison of differentiated cells after culture with ertugliflozin vs control vehicle), 8 subjects are needed for similar statistical power using a paired student's t-test. Cell culture with ertugliflozin vs control vehicle: in order to attain statistical power for testing direct actions on VAT and SAT from a given subject (comparison of differentiated cells after culture with ertugliflozin vs control vehicle), 14 subjects are needed for similar statistical power using a paired student's t-test. Measurement of phosphorylated hormone-sensitive lipase (pHSL/HSL ratio reflects HSL activity) will comprise supportive data (in vivo study) for this endpoint and it is expected that ertugliflozin will increase HSL activity, consistent with increased lipolysis.

Secondary endpoint: Inflammatory cytokine expression:

In a prior study ([name] & Engleman, Arteriosclerosis, Thrombosis, and Vascular Biology. 2014;34:2637–2643) in which we measured relative gene expression of inflammatory cytokines in subcutaneous vs visceral fat we found a difference of 1.4 (fold expression) with SD of 1.4, again yielding a number of 5 subjects per group for 80% power and alpha 0.05 for unpaired student's t-test (two-tailed). Cell culture with ertugliflozin vs control vehicle: in order to attain statistical power for testing direct actions on EAT from a given subject (comparison of differentiated cells after culture with ertugliflozin vs control vehicle), 8 subjects are needed for similar statistical power using a paired student's t-test. Cell culture with ertugliflozin vs control vehicle: in order to attain statistical power for testing direct actions on VAT and SAT from a given subject (comparison of differentiated cells after culture with ertugliflozin vs control vehicle), 14 subjects are needed for similar statistical power using a paired student's t-test. Secretome in the supernatant (cell culture and in vivo study) will comprise supportive data.

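### In the 14-day culture the drug is present throughout differentiation, so day-14 glucose uptake and inflammatory expression mix a change in the share of adipocytes with a change in function per adipocyte

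*Combined protocol and SAP*

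**What the plan says.** **Exposure.** Section 5 (preadipocyte differentiation) seeds stromal-vascular cells in "12-well plates at a density of 10,000 cells per well for assessment of adipogenesis". It then states that "ERTUGLIFLOZIN and vehicle are supplemented to the adipogenic differentiation medium". At day 3 the medium changes to maintenance medium "and ertugliflozin is supplemented". "Differentiation is carried out for 14 days to achieve terminal differentiation". No method describes differentiating without drug and exposing the cells afterwards.

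**Readouts.** Section 7 measures IMGU in these cells after the 14 days: "Each samples fluorescence reading is normalized by its protein concentration as the final reading". Section 3 takes RNA from frozen tissue or from terminally differentiated cells at day 14, normalised to GAPDH/18S. Section 12 normalises cytokines in culture medium to the number of cells seeded.

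**Differentiation.** It is measured by Oil Red O (section 8), by the percentage of lipid-stained cells over nuclei (section 9) and by marker genes (section 3). The last line of Statistical Plans gives it its own t-test, alongside IMGU.

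**Statistical comparison.** For both the primary and the secondary endpoint, Statistical Plans describes the paired test of direct actions as a "comparison of differentiated cells after culture with ertugliflozin vs control vehicle", with 8 subjects for epicardial fat (EAT) and 14 for visceral and subcutaneous fat.

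**Background and Rationale.** "EAT preadipocytes cultured with dapagliflozin demonstrated enhanced differentiation, decreased chemokine secretion, and increased glucose uptake".

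**Study Design, item 2.** Mature cells from bariatric samples are tested for lipolysis, IMGU, "gene expression, and inflammatory cytokine secretion under mock vs drug-treated culture conditions for 2-24 hours". When EAT is scarce, stromal-vascular cells are to be differentiated to supply a lipolysis assay. The drug exposure for that fallback is not given.

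**The concern.** A treatment present while the cells are becoming adipocytes can act in two ways: it can change how many cells differentiate, and it can change what each adipocyte does. A reading per unit of protein, or per unit of housekeeping RNA, corrects for the amount of material in the well but not for its composition.

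The protocol itself makes a composition effect plausible. It cites enhanced differentiation with a related drug, and it makes differentiation an endpoint. Pairing within donor does not help, because the drug causes the imbalance within each pair.

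At stake is how two results are read. The Hypothesis section concerns adipocytes that are more insulin-sensitive and less inflamed. A higher day-14 IMGU could instead mean more adipocytes per unit of protein. A changed cytokine transcript level could mean a different mix of adipocytes and precursors. A true change per adipocyte could also be hidden.

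**Working it through.** **1. Trace of each readout**

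| Readout | Drug exposure in the text | Denominator | Mixed with composition? |
|---|---|---|---|
| Cultured-cell IMGU (section 7) | through the 14-day culture | total protein | yes |
| Cultured-cell inflammatory RNA (section 3) | through the 14-day culture | GAPDH/18S | yes |
| Differentiation measures (sections 8, 9) | through the 14-day culture | as designed | no; this is the target |
| Fresh mature cells (sections 10, 11) | 2-24 h (Study Design, item 2) | not relevant here | no |
| Explants (section 17) | overnight | not relevant here | no |
| Lipolysis in differentiated stromal-vascular cells (Study Design, item 2) | not stated | not stated | only if section 5 applies |

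**2. Size for IMGU (illustrative)**

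Let p be the differentiated share and f the function per adipocyte relative to vehicle. Let r be the signal of an undifferentiated cell relative to a vehicle adipocyte. Assume protein per cell is similar. The protein-normalised ratio of drug (1) to vehicle (0) is

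R = [p1·f + (1 − p1)·r] / [p0 + (1 − p0)·r].

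The documents give none of these values. Assume p0 = 40% and no change per adipocyte (f = 1).

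- With r = 0, R = p1/p0: 44/40 = 1.10, 50/40 = 1.25, 60/40 = 1.50.
- With r = 1, R = 1.00 in each case.

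The bias therefore runs from none up to 10%, 25% or 50%, depending on what undifferentiated cells contribute. Opposite movements can cancel: with r = 0, a 20% higher share and 20% lower function give 1.20 × 0.80 = 0.96, which reads as −4%.

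**3. What dividing by the differentiated share does**

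With f = 1 and r = 0, R/(p1/p0) = 1, which is correct. With f = 1 and r = 1, the divided ratio is 40/44 = 0.91, 40/50 = 0.80 or 40/60 = 0.67, which is an over-correction. Division alone is therefore not safe, and both versions need to be shown.

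**4. The plan's paired sample size**

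The secondary endpoint has a difference of 1.4 and an SD of 1.4; the primary has 0.2 and 0.2. The ratio is 1 in both. The SD of paired differences is not given; assume it equals the stated SD. Then

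n = (1.960 + 0.842)² × 1² = 7.85, rounded up to 8.

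This reproduces the 8 for EAT. By the exact paired t-test, n = 10 is needed, and power at 8 is 68%.

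**5. Chance that a composition shift alone is significant**

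Same SD assumption, two-sided 0.05, no effect per adipocyte:

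| Shift as share of the planned difference | n = 8 | n = 14 |
|---|---|---|
| 25% | 9% | 14% |
| 50% | 23% | 41% |
| 75% | 45% | 74% |
| 100% | 68% | 93% |

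The shifts are assumed. The table applies to inflammatory expression, and to lipolysis only if the fallback uses the 14-day exposure. The plan gives no difference or SD for IMGU.

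**The case against.** Several stronger readings are tempting, and the documents do not support them.

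- **That the primary lipolysis endpoint is confounded.** The written lipolysis methods cover fresh mature cells and explants only. The fallback for scarce EAT does not say that drug is present during differentiation; differentiating first and treating afterwards fits its wording equally well. What stands is that the exposure is unstated, while Statistical Plans names differentiated cells in the primary comparison.
- **That 14 days contradicts the 2-24 hour window.** Fourteen days is 336 h, or 14 to 168 times that window (336/24 and 336/2). But the window is written for explants and mature cells, not for this arm. The ratio shows that the two experiments ask different questions; it does not show an error.
- **That drug should not be present during differentiation.** Section 5 exists to assess adipogenesis, and for that purpose the design is suitable. Study Design treats an effect as direct when the systemic changes are absent, so altered differentiation in vitro is a direct effect in that sense. It is still not the same as more insulin-sensitive adipocytes, which is what the Hypothesis states.
- **That the results would be uninterpretable.** Differentiation is measured, so a careful reader could see a shift. However, no analysis links it to the functional results.

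Two further objections stand. The 40% baseline and the shifts from it are assumed. Zero contribution from undifferentiated cells maximises the bias, and section 7 describes no well without insulin from which basal uptake could be separated.

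**Conclusion.** The point holds for two day-14 readouts in the cultured-cell arm: IMGU per unit of protein and inflammatory expression per GAPDH/18S. As planned, neither can separate a change in the share of adipocytes from a change in function per adipocyte.

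The size is unknown. Under the assumed 40% baseline it ranges from nothing up to 10%, 25% or 50% for IMGU. The size and direction for expression cannot be derived from the documents. A composition shift of half the planned expression difference would be significant in 23% of studies at n = 8, if the SD of paired differences equals the stated SD.

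A reader might infer that the whole direct-effect programme, or the primary endpoint, is undermined. It is not: explant and fresh-cell results are untouched, and lipolysis is at risk only through the fallback whose exposure is not stated. This is a point about analysis and interpretation, and it changes no sample size.

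**What to change.** 1. For day-14 cultured-cell functional and inflammatory endpoints, report the paired drug-versus-vehicle comparison as planned. Beside it, report the same comparison divided by, or adjusted for, the section 9 percentage differentiated in sister wells of the same donor and condition. For expression, adjustment is more natural than division, because section 12 treats preadipocyte cultures as a source of cytokines too.
2. Describe the unadjusted result as the effect of differentiating under drug, not as enhanced function of mature adipocytes.
3. Where cell yield allows, add wells differentiated without drug and then exposed to mock or drug within the 2-24 hour window already stated in Study Design. Keep the 14-day drug wells for the differentiation endpoints.
4. Reconcile Study Design item 2, Laboratory Methods section 5 and Statistical Plans on the exposure of differentiated cells used for lipolysis.

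**Cost.** Items 1 and 2 use counts already planned and can be applied to completed cultures that have section 9 wells. Section 9 fixes the cells and section 7 lyses them, so the denominator must come from different wells, which adds measurement noise at n = 8. Item 3 needs a few more wells of 10,000 cells per donor and depot, and EAT yield may not allow it. Item 4 is text only.

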Our laboratory has vast experience in working with human adipose tissue/cell metabolism, inflammation, morphology, and differentiation. We have established a working relationship with the cardiac surgery team and recently completed a study in 24 subjects with myocardial bridge, in whom we sampled five fat depots, including three from the epicardium, over vessels with and without atherosclerotic plaque. Gene expression (60 genes via Nanostring) and cytokine secretion analyses are in process. We also have spent over a decade performing collagenase digestion of subcutaneous and visceral human fat to isolate mature adipocytes for measurement of insulin-mediated glucose uptake (IMGU) and lipolysis, and stromal-vascular cells for flow cytometry and preadipocyte differentiation (methods published). We thus have the infrastructure, interdisciplinary relationships, wet lab space and methods, and scientific expertise in adipocyte biology and metabolism to investigate the effects of ertugliflozin on epicardial fat. We hypothesize that ertugliflozin will enhance lipolysis, improve insulin sensitivity, decrease adipose cell size, and reverse inflammatory phenotype in EAT.

References

3. [name], Carter S, Lamendola C, et al. Effects of moderate variations in macronutrient composition on weight loss and reduction in cardiovascular disease risk in obese, insulin-resistant adults. *Am J Clin Nutr* 2006; 84:813-21.
4. [name] et al. Effect of Low Carbohydrate Weight Loss Diet on Adipose Cell Size. 1709P. American Diabetes Association 2016, New Orleans, LA.
5. Iacobellis G. Local and systemic effects of the multifaceted epicardial adipose tissue depot. *Nat Rev Endocrinol*. 2015; 11:363-71.

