Oil red O staining and quantification are performed after two weeks of differentiation. Briefly, differentiated cells are fixed with 10% formalin in PBS, Oil Red O solution (Sigma, Inc) is used to stain the cells. After washing, stained cells will be dried at room temperature and photos will be taken by light microscope. To extract and quantify the cell staining, we use 100% isopropanol and subtract the background signal. Readings of absorbance at 492 nm are calculated compared to control¹⁷.

9) % Differentiation using immunofluorescence on day 14 culture

Briefly, terminal differentiated cells after two weeks are fixed in 4% glucose/paraformaldehyde in PBS solution (made for freshly use) for one hour and stain with DAPI (blue) and Bodipy FL (ER-Tracker Green) in 37C for two hours. Fluorescence microscope is used to capture the lipid droplets of green staining with internal control of DAPI (nuclei staining). Photos are counted using NIH imagine J software. The total Green stained cells or percent of green cells will be counted normalized by the blue staining of nuclei numbers as the differentiated cells^{17,18}.

10) Basal and isoproterenol-stimulated lipolysis on mature adipocytes isolated via collagenase digestion

Lipolysis assay is carried out by using Lipolysis Colorimetric Assay Kit (Biovision, Inc.), Cat# K577-100 as described⁴. Briefly, the washed mature cells (in PCV) are diluted into 1:2 in Lipolysis Assay Buffer based on manufacturer's protocol. A glycerol standard is built with supplies offered in the kit and a colorimetric assay is performed with human mature cells mixture and glycerol standard at the same time in 96-well reaction. Afterwards, cells are incubated with 100nM of isoproterenol (set to induce the glycerol release) for 3 hours at room temperature. Glycerol standard and mature cells suspension are measured at OD of 570nm. Based on the standards, the mature cell glycerol amount can be calculated.

11) IMGU using 2NDBG for mature adipocytes isolated via collagenase digestion

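### The preadipocyte cultures use an ertugliflozin level chosen for halving growth, and two of their readouts cannot separate fewer cells from a drug effect per cell

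*Combined protocol and SAP*

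**What the plan says.** All places are in the combined protocol and SAP.

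- **Scope of the rule.** Item 6 of the Laboratory Methods is headed "Optimization of ertugliflozin concentration for pre-adipocyte culture studies".
- **Levels and growth readout.** "Planned concentrations to test include 10, 100 and 300nmol/L", beside a vehicle control. "BrdU can be used to determine the proliferation effect at day 3 and day 7".
- **Selection rule.** "Optimal concentration will be defined as the concentration that yields 50% of growth inhibition". The item gives no reason for the criterion, no viability check and no fallback.
- **Exposure.** Item 5 (preadipocyte differentiation) states "ERTUGLIFLOZIN and vehicle are supplemented to the adipogenic differentiation medium" and continues the drug in the maintenance medium up to day 14. It names no concentration.
- **Hypotheses.** The Background closes with "We hypothesize that ertugliflozin will enhance lipolysis, improve insulin sensitivity, decrease adipose cell size, and reverse inflammatory phenotype in EAT". The Hypothesis section is in the same terms. Neither mentions proliferation.
- **Readouts of these cultures.** Glucose uptake (item 7): "Each samples fluorescence reading is normalized by its protein concentration as the final reading". Oil Red O (item 8): "Readings of absorbance at 492 nm are calculated compared to control", after background subtraction. Percent differentiation (item 9) is relative to nuclei, and gene expression (item 3) is relative to GAPDH/18S. The preadipocyte secretome (item 12), sampled on days 3, 7 and 14, is divided by the number of attached cells at seeding.

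**The concern.** Choosing the level that halves growth suits a study of an anti-proliferative agent. Here the question is whether the drug acts directly on fat-cell metabolism and inflammation, so the rule optimises for an effect that no hypothesis seeks.

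Two problems follow. First, the rule may not give an answer: no planned level may reach 50%, or day 3 and day 7 may point to different levels. Second, if it does give an answer, drug and vehicle wells differ in proliferation by construction. A readout that scales with the number of cells in the well, and is not corrected for that number at the time of measurement, then falls even if each cell behaves exactly as under vehicle. For cytokines the fall is in the hypothesised direction. For Oil Red O it would look like less fat taken up or stored. Either could be reported as a direct drug effect.

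**Working it through.** The plan derives no sample size or power from this rule, so there is no stated figure to reproduce. The check has three parts.

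**1. Which readouts are exposed**

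| Readout in preadipocyte cultures | Divided by | Corrects for cell number at measurement? |
|---|---|---|
| Glucose uptake (item 7) | protein | largely |
| Gene expression (item 3) | GAPDH/18S | largely |
| Percent differentiation (item 9) | nuclei | largely |
| Oil Red O (item 8) | nothing stated | no |
| Secretome (item 12) | cells at seeding | no; fixed before growth can differ |

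**2. Size of the artefact**

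Signal per well = cells × signal per cell. With signal per cell unchanged, the drug-to-vehicle ratio is f = 1 − 0.5c, where c is the share of the 50% growth deficit still present as a deficit in cell number at measurement. The plan gives no c, so the range is an assumption:

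- c = 1: f = 1 − 0.50 = 0.50
- c = 0.5: f = 1 − 0.25 = 0.75
- c = 0.25: f = 1 − 0.125 = 0.875

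The middle value also arises another way. If growth means net gain and vehicle cells double, drug wells reach 1 + 0.5 = 1.5 against 2, and 1.5/2 = 0.75.

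**3. Chance that the artefact alone is significant**

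The Statistical Plans section analyses other endpoints by unpaired and paired t-tests. It gives paired samples of 8 (EAT) and 14 (VAT and SAT) for cultured cells. I assume the same numbers apply to these two readouts. For a two-sided paired test at 0.05 on the log scale, the standardised difference is |ln f|/s, where s is the SD of the paired log difference. The plan gives no s, so I take 0.3 to 1.0. For example, f = 0.50 and s = 0.5 give 0.693/0.5 = 1.386. At n = 8 the noncentrality is 1.386 × √8 = 3.92, and the probability of significance from the noncentral t is 0.92.

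| f | n | s = 0.3 | s = 0.5 | s = 0.7 | s = 1.0 |
|---|---|---|---|---|---|
| 0.50 | 8 | >0.99 | 0.92 | 0.67 | 0.40 |
| 0.50 | 14 | >0.99 | >0.99 | 0.93 | 0.67 |
| 0.75 | 8 | 0.65 | 0.29 | 0.17 | 0.11 |
| 0.75 | 14 | 0.91 | 0.51 | 0.30 | 0.17 |

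Without any artefact each entry would be 0.05. At f = 0.90 the n = 8 values are only 0.14 down to 0.06, so a small carry-through does little harm.

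**Reach of the rule.** Item 17 treats explants overnight at 25 µM. That is 25,000/300 = 83 times the highest level in item 6 and 25,000/10 = 2,500 times the lowest, so explants are not run at the item 6 level. The Study Design section treats isolated mature adipocytes for 2 to 24 hours and makes no link to item 6.

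**The case against.** The strongest reply is that little of the study rests on this rule. Most direct-effect work described in the Study Design section uses explants and isolated mature adipocytes. Differentiating stromal-vascular cells for lipolysis is the plan's recourse when EAT is scarce. The secondary endpoint, cytokine expression, is normalised to housekeeping genes. Oil Red O is neither primary nor secondary, and the secretome is called supportive. This stands, and it limits the point to the preadipocyte cultures and, within them, to two readouts.

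The confounding is also conditional. The documents contain no data showing that any of the three levels halves growth. Half the growth need not mean half the cells. Item 3 speaks of day 14 after confluence, which suggests that density may partly even out. This also stands, and it is why the size is given as a range.

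Three stronger readings are tempting but not supported:

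- **All culture work is run at a growth-inhibiting level.** The heading of item 6 restricts the rule, and item 17 uses a different concentration.
- **The drug kills cells.** BrdU is a proliferation readout, and the plan neither measures nor states cell death. Fewer cells is as far as the text goes.
- **The primary lipolysis comparison is biased.** The Statistical Plans section does refer to differentiated cells, but it expresses the target difference per µg protein per hour. The two written lipolysis methods (items 10 and 17) concern isolated mature cells and explants. What remains is an omission: no lipolysis method is written for differentiated cells, and item 10 stops at a glycerol amount. The protein correction should therefore be stated.

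Normalisation does not remove changes within cells caused by lower density or stress. That possibility remains for every readout of these cultures, but the documents give no means of sizing it.

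**Conclusion.** The concern holds for the preadipocyte cultures only. The selection criterion is unrelated to the hypotheses, is unexplained, and is incomplete where no level reaches 50% or the two days disagree. If a level does halve growth, Oil Red O and the preadipocyte secretome can fall to between 0.50 and 0.875 of vehicle with no drug effect per cell. At the upper end of that artefact, a paired test in 8 donors would be significant with probability 0.40 or more over the assumed SDs.

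This rests on three assumptions: that the item 6 level is the one used in item 5, which the heading strongly implies but item 5 does not state; that one quarter to all of the growth deficit persists as a deficit in cell number; and, for the probabilities, the log SDs and donor numbers above. Gene expression, cultured-cell glucose uptake and percent differentiation are largely protected.

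**What to change.** 1. **Item 6.** Replace the 50% target with an exclusion check: a planned level qualifies only if BrdU growth stays within a margin of vehicle on both day 3 and day 7. The investigators set the margin in advance. State what happens if no level qualifies.
2. **Selection.** Choose among the qualifying planned levels on a hypothesis-relevant readout, in wells or donors outside the confirmatory comparison, or report all qualifying levels.
3. **Items 8 and 12.** Express Oil Red O and preadipocyte cytokines per end-of-culture protein or nuclei. The protein assay is already in item 7 and the nuclear stain in item 9.
4. **Cross-references.** State in item 5 which concentration is used, and state the lipolysis method and its protein correction for differentiated cells. Reconcile the item 6 range with the 25 µM in item 17, or explain the difference. No concentration is proposed here.
5. **If the cultures are complete.** This is plausible, since the September 2024 update reports 61 enrolled against a goal of 36. Report the concentration used and its measured growth effect, and renormalise where protein or nuclei data exist. Otherwise make no direct-effect claim from these two readouts.

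The cost is a few more wells, additional protein or nuclei readings, and some pilot material kept apart. The last is a real constraint where EAT is scarce, and selecting on differentiated cells takes a further 14-day culture. Reporting all qualifying levels avoids the separate pilot, but needs more wells per donor and a stated way of handling several comparisons.
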